- 11 See Table E: Non-intensive Sampling Days for PD measures and timepoints and Table L: Research Sample Collection.
- See Table E: Use Non-intensive Sampling Days schedule for PK timepoints.
- 13 See Table E: see time intervals for urine collections for calculation of fractional excretion rates and 24-hour total excretion of urine Ca, Mg, PO4, Cr, cAMP, citrate, Na, K, pH during the NIH CC visits
- Outpatient 24-hr urine Ca, Mg, PO4, Cr, Na, K, citrate, pH at 20 weeks. Participants who withdraw from taking CLTX-305 (encaleret) (EoT) before completing Period 3 per protocol or chose not to continue into the LTE will obtain 24-hr urine at 30 ± 7 days follow-up.
- Week 24 drug dispensing is only for participants who continue into the LTE; If a participant is not immediately continuing into the LTE, no drug will be dispensed.

 Table D
 Long-term Extension Schedule of Activities

LTE - A	outpatient labs  2 to 3 ± 2 days	J outpatient labs  $7 \pm 2$ days	FU- after last dose  $30 \pm 7$ days	Un-scheduled visit³										
	Study Dosing Period													
Months 	NIH CC		NIH CC		NIH CC		NIH CC		NIH CC EoT/ET 					
wionths -	013	3	6	9	12	15	18	21	24					
Days (windows)		± 7	± 7	±7	± 7	±7	±7	±7	+30					
Reconsent 	X													
Telephone Contact (NIH PI/Study Staff)		X		X		X		X		X	X	X	X	
AEs and SAEs, Con meds	X	←							<del>-</del>	X	X	X	X	
Review compliance  /dose adjustment as needed		X	X	X	X	X	X	X	X					
Outpatient laboratory 		X		X		X		X		X	X	X		
NIH CC visit			X		X		X		X					
Renal ultrasound, DXA scan					X				X 					
Dispense study drug	X		X		X		X							
Height  and weight			X		X		X		X					
Vital signs 			X		X		X		X					
Physical examination			X		X		X		X					
Safety and Drug Monitoring Laboratory 	X 		X		X		X		X					
Blood β-HCG pregnancy test (WOCBP only) 			X		X		X		X					
ECG, 12-lead			X		X		X		X					
Study drug administration 	X	←						→						
24-hour Urine 		X	X	X	X	X	X	X	X			X 		

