- Document current CLTX-305 (encaleret) dose and calcium dosing regimen, any modifications, and reason for modifications
- Outpatient laboratory testing: Blood samples for clinical laboratory panels (Na, Cl, bicarbonate, K, BUN, Cr and including Alb, Ca, Mg, PO4, iPTH, CTX, and P1NP).
-  Height measured only at month 24/final visit or ET visit
- Vital signs include supine or sitting blood pressure (BP) by automated cuff, heart rate (HR), and respiratory rate.
- Safety and Drug Monitoring Labs collected at the NIH CC visits approximately 4 hours after the morning encaleret dose Chemistry (Na, K, Cl, bicarbonate, Glu, BUN, Cr, Alb, total protein, Ca, Mg, PO4, iPTH, 25-OH Vitamin D, CTX, P1NP, Cholesterol, TG, AST, ALT, Tbili, Alk phos, LDH, amylase, lipase, uric acid, CK), Hematology (RBC, Hgb, Hct, RBC indices, WBC, diff), Coagulation (PT/PTT/INR), Research labs (FGF23 and mid-molecule PTH). HIV, viral hepatitis panel should be repeated within 3 months prior to transition to CLTX-305-302/CALIBRATE.
- 9 Blood β-HCG pregnancy test can be performed at the NIH CC on the day of transition to CLTX-305-302/CALIBRATE Phase 3 LTE, and an aliquot will also be sent to the central lab for the CLTX-305-302/CALIBRATE Phase 3 LTE.
-  CLTX-305 (encaleret) administered and recorded during the NIH CC visit/in-house days.
- Outpatient 24-hr urine collection for Ca, Mg, PO4, Cr, Na, K, citrate, pH
- A final follow-up safety telephone call and outpatient labs will occur 30 ± 7 days after the last dose of CLTX-305 (encaleret).
- 13 If a participant is not able to enter the LTE immediately following Period 3, then participant will be reconsented to and may restart CLTX-305 (encaleret) at the previous therapeutic dose determined in Period 3. Safety and Drug Monitoring Laboratory tests should be done while participant is at the NIH CC.
- When participant transitions to CLTX-305-302/CALIBRATE Phase 3 LTE, participant will be asked to return to the NIH CC to return the unused CLTX-305 (encaleret), and complete any remaining eligibility assessments for the CLTX-305-302/CALIBRATE Phase 3 LTE study.
- 15 If the Month 24 visit aligns with the transition to the CLTX-305-302/CALIBRATE Phase 3 LTE, then the renal ultrasound and DXA scan will be performed once as part of the CLTX-305-302/CALIBRATE Phase 3 LTE.

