The first 7 participants who have completed CLTX-305-201 Period 2 and entered into Period 3 have had a wide range of CLTX-305 (encaleret) dose requirements from 10 mg once daily to 180 mg BID suggesting that CLTX-305 (encaleret) dosing is highly individualized. As a result, all remaining participants in Period 2 will receive an initial CLTX-305 (encaleret) 90 mg BID dose for at least 3-4 doses for evaluation of safety, tolerability and the ability to modulate cCa levels. The CLTX-305 (encaleret) dose will be up- or down-titrated as needed to maintain cCa levels below 10 mg/dL and blood phosphorus levels above the lower limit of normal. Dosing will be adjusted in 5, 10, 30, or 60 mg increments based on the available CLTX-305 (encaleret) tablet strengths. A frequent sampling test day with additional serial blood and urine sampling to assess 24-hour PK/PD profiles will be performed on Day 5. For details on the PK/PD timepoints during frequent sampling on Day 5 see Section 1.3.1 specifically Table J and Table K.

The total blood volume collected during Period 2 for Cohort 1 participants will be less than the blood volume limits per participant as per NIH Guidelines for Blood Draw Limits for Research Purposes (M95-9, June 2009). These volumes include the cumulative potential collection over an 8-week period: -10-14-day labs, Day -1 safety labs, Period 2 inpatient week, and 4 weeks of outpatient labs in Period 3. If a participant has a low body weight (<43 kg for adults or <48 kg for adolescents), the blood volume taken will be reduced to remain within the NIH guidelines of 10.5mL/kg/8w (adult) and 9.5 mL/kg/8w (pediatric). If, at any time, the CLTX-305 (encaleret) dose is associated with a cCa > 10 mg/dL, then the dose should be reduced to a lower dose level. An example of how CLTX-305 (encaleret) dosing may be adjusted is provided in Figure F below.

Figure F Dosing Guidance Algorithm for Period 2 – Cohort 1

BID= Two doses/day

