Study visits include inpatient NIH Clinical Center visits every 8 weeks. PK assessments will be done at week 24 only; PD assessment will be done at weeks 8, 16 and 24 for evaluation of safety. AEs and concomitant medications will be recorded during these visits. Participants will be contacted by telephone per protocol at intervals during titration and maintenance, to

review the results of outpatient laboratory blood and urine assessments, confirm adequacy of the current regimen of study medication (including supplements), inquire about hypo/hypercalcemia symptoms, and assess for AEs. Participants are considered to have completed the study once they complete 24 weeks of Period 3 and the safety follow-up visit.

For details on the visit schedule and assessments in Period 3 see Section 1.3.

The total blood volume collected over 24 weeks during Period 3 for each participant will be less than the blood volume limits per participant as per NIH Guidelines for Blood Draw Limits for Research Purposes (M95-9, June 2009). This includes the 3 inpatient NIH visits.

If a participant reaches week 24 prior to the LTE being in place, the participant can discontinue CLTX-305 (encaleret) and restart calcitriol and/or calcium supplements until the LTE is implemented. Upon entry into the LTE, the participant will be reconsented to and may restart CLTX-305 (encaleret) at the previous therapeutic dose determined in Period 3.

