4.1 Overall Study Design	Change the maximum number of participants in Period 2 from	Increase the maximum number of
9.2 Sample size	up to 8 additional participants to up to 10 participants	participants in Period 2
6.1.7 Dose Modifications	Added guidance language for dose interruption and dose	Information added related to dose
	resumption	interruption and continuation
8.4.3 Clinical Laboratory	Information added on reporting of laboratory AEs resulting in	Clarification related to reporting
Determinations	clinical intervention	laboratory AEs
8.4.4 Electrocardiograms	added additional ECG measurement during Period 2	Added additional ECG measures
		for safety
10.6 Clinical Monitoring	Option for virtual/remote monitoring visits added	Flexibility for onsite or virtual
10.8.1 Data Collection and		study monitoring visits in
Management		consideration to COVID-19
Responsibilities		pandemic limitations
Section No./Title	Amendment 6: Date 03 June 2021	Rationale
All sections of the protocol	Replaced: references of study subjects to study participants	General Administrative change:
	throughout the documents	Consistency of terms used
		throughout the protocol
All sections of the protocol	Replaced: CLTX-305 with CLTX-305 (encaleret)	General Administrative change:
		Consistency of terms used
		throughout the protocol
Protocol Cover page	Calcilytix address has changed, new address is inserted as:	Updated- Sponsor change of
	[name]	address
D 4 1.C	[name]	
Protocol Cover page The Spanger Signature page	Contact Information for the new Sponsor	Updated pertinent sections of the
The Sponsor Signature page	added:	protocol to reflect name and

Section No./Title	Changes	Rationale
8 Study assessment and procedure 8.5 Adverse Events and Serious Adverse Events	Telephone: Calcilytix Therapeutics, Inc. [name] [name]	contact information for the

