10.7 Prior and Concomitant Medications

As there will be no interruption of study drug treatment between Period 2, Period 3 and LTE, those 3 periods will be considered only one period and referred to Period 2 in the below definitions.

Prior Medications – Period 1

For subjects in cohort 1, prior medications or supplements will be any medications or supplements with a start date before the start of treatment on Study Day 1.

Prior Medications – Period 2

For subjects in cohort 1, prior medications or supplements will be any medications or supplements with a start date after the end of treatment from Period 1 and before the start of treatment in Period 2.

For subjects in cohort 2, prior medications or supplements will be any medications or supplements with a start date before the start of treatment on Study Day 1.

Concomitant Medications – Period 1

Concomitant medications are defined as any medications ongoing at the Period 1 start of treatment (i.e. medications which started before the Period 1 start of treatment and are recorded as ongoing or

with a stop date after the Period 1 start of treatment) or with a start date on or after the Period 1 start of treatment, but on or prior to the Period 1 end of study treatment + 30 days

Concomitant Medications – Period 2

Concomitant medications are defined as any medications ongoing at the Period 2 start of treatment (i.e. medications which started before the Period 2 start of treatment and are recorded as ongoing or with a stop date after the Period 2 start of treatment) or with a start date on or after the Period 2 start of treatment, but on or prior to end of study treatment + 30 days.

Each medication is mapped to a Period based on their start date and as per the rules defined in Table 1. If the start date is partial, determination of the Period will be based on the imputed start date (see Section 10.11 for details). If the date is entirely missing, the medication will be assigned to Period 1 for subjects in Cohort 1 and to Period 2 for subjects in Cohort 2.

Period	Prior	Concomitant
Period 1	Medications with start date/time	Medications with start date/time on or after Period 1 Day 1 and prior to the Period 2 Day 1 AM dose
	prior to Period 1 Day 1	Medications with start date/time prior to Period 1 Day 1 and end date/time on or after Period 1 Day 1/ongoing

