10.8 Treatment-emergent Adverse Event (TEAE)

For subjects in Cohort 1, AEs will be considered treatment-emergent to Period 1 if they have missing or partial start dates for which it cannot be determined whether the AE started before or after the Period 1 or Period 2 first dose of study medication.

For subjects in Cohort 2, AEs will be considered treatment-emergent to Period 2 if they have missing or partial start dates for which it cannot be determined whether the AE started before or after the Period 2 first dose of study medication.

As there will be no interruption of study drug treatment between Period 2, Period 3 and LTE, those 3 periods will be considered only one period and referred to Period 2 in the below definitions.

Period 1

Treatment-emergent AEs (TEAEs) are defined as any AE(s) or SAE(s), regardless of relationship to study drug, that have an onset or worsening in severity on or after the first dose of study drug until 30 days after Period 1 last dose of treatment date.

Period 2

TEAEs are defined as any AE(s) or SAE(s), regardless of relationship to study drug, that have an onset or worsening in severity on or after the Period 2 first dose of study drug until 30 days after the last dose of treatment in the study.

Each AE is mapped to a Period based on their start date, using the rules defined in Table 2. If the start date is partial, determination of the Period will based on the imputed start date (see Section 10.11 for details). If the date is entirely missing, the AE will be assigned to Period 1 for subjects in Cohort 1 and to Period 2 for subjects in Cohort 2.

Cohort	Analysis Period	Start of the Period	End of the Period
	1*	Data of ICE	If the subject continued in Period 2: last dose in Period 1 + 30 days.
	1.	Date of ICF	If the subject did not continue in Period 2: all AEs are assigned to Period 1.
1	2	Date of Outpatient	If the subject continued in Period 3: last dose in Period 2.
	2	Admission Visit	If the subject did not continue in Period 3: Date of completion/discontinuation of the study
	3	Last dose date in Period 2 + 1 day	If the subject continued in LTE: last dose in Period 3.
			If the subject did not continue in LTE: Date of completion/discontinuation of the study
	LTE	Last dose date in Period 3 + 1 day	Date of completion/discontinuation of the study
	2		If the subject continued in Period 3: last dose in Period 2.
2	2	Date of ICF	If the subject did not continue in Period 3: all AEs are assigned to Period 2.

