- ³ Unscheduled visits: For laboratory evaluation following dose adjustment or assessment or follow-up of an AE, in which clinically indicated procedures will be performed
- ⁴ Document current CLTX-305 (encaleret) dose and calcium dosing regimen, any modifications, and reason for modifications
- ⁵ Outpatient laboratory testing: Blood samples for clinical laboratory panels (Na, Cl, bicarbonate, K, BUN, Cr and including Alb, Ca, Mg, PO₄, iPTH, CTX, and P1NP).
- ⁶ Height measured only at month 24/final visit or ET visit
- ⁷ Vital signs include supine or sitting blood pressure (BP) by automated cuff, heart rate (HR), and respiratory rate.
- ⁸ Safety and Drug Monitoring Labs collected at the NIH CC visits approximately 4 hours after the morning encaleret dose Chemistry (Na, K, Cl, bicarbonate, Glu, BUN, Cr, Alb, total protein, Ca, Mg, PO4, iPTH, 25-OH Vitamin D, CTX, P1NP, Cholesterol, TG, AST, ALT, Tbili, Alk phos, LDH, amylase, lipase, uric acid, CK), Hematology (RBC, Hgb, Hct, RBC indices, WBC, diff), Coagulation (PT/PTT/INR), Research labs (FGF23 and mid-molecule PTH). HIV, viral hepatitis panel should be repeated within 3 months prior to transition to CLTX-305-302/CALIBRATE.
- ⁹ CLTX-305 (encaleret) administered and recorded during the NIH CC visit/in-house days.
- ¹⁰ Outpatient 24-hr urine collection for Ca, Mg, PO4, Cr, Na, K, citrate, pH
- ¹¹ A final follow-up safety telephone call and outpatient labs will occur 30 ± 7 days after the last dose of CLTX-305 (encaleret).
- ¹² If a participant is not able to enter the LTE immediately following Period 3, then participant will be reconsented to and may restart CLTX-305 (encaleret) at the previous therapeutic dose determined in Period 3. Safety and Drug Monitoring Laboratory tests should be done while participant is at the NIH CC.
- ¹³ When participant transitions to CLTX-305-302/CALIBRATE, participant will be asked to return to the NIH CC to complete the ET/EoT visit assessments, return the unused CLTX-305 (encaleret), and complete the screening assessments for the CLTX-305-302/CALIBRATE Phase 3 study. Follow-up labs will not be needed.

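### SAP 10.8 assumes no drug gap before the LTE, but the plan allows a stop at Week 24 and a later restart; every dated AE in such a gap would count as an LTE TEAE

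*SAP*

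**What the plan says.** SAP 10.8, with the same sentence in 10.7, gives this reason for treating Period 2, Period 3 and the LTE as one period: "As there will be no interruption of study drug treatment between Period 2, Period 3 and LTE". The TEAE window for the pooled period runs from the first Period 2 dose to 30 days after the last dose in the study. Table 2 starts the LTE, for AE mapping, on the day after the last Period 3 dose.

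The protocol allows the interruption that this premise excludes. Under 8.2.3, if Week 24 is reached before the LTE is in place, "the participant can discontinue CLTX-305 (encaleret) and restart calcitriol and/or calcium supplements until the LTE is implemented". Table C note 15 adds: "If a participant is not immediately continuing into the LTE, no drug will be dispensed". Table D note 13 provides for the later entry: "If a participant is not able to enter the LTE immediately following Period 3", the participant is reconsented and may resume treatment. The SAP carries the same provisions in its appendix. Table 10 note 15 repeats the dispensing note, and Table 11 note 12 says that the participant "may restart CLTX-305 (encaleret) at the previous therapeutic dose determined in Period 3".

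For the planned gap between Periods 1 and 2, SAP 13.6.1 and the Table 2 footnote say that AEs more than 30 days after the last Period 1 dose and before Period 2 are not treatment-emergent and are listed separately.

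**The concern.** A rule built on a premise that the plan elsewhere lets fail gives a wrong result when it does fail. During a gap the participant is off encaleret and back on calcitriol and/or calcium, yet the pooled window stays open and Table 2 has already started the LTE. AEs from that time would be reported as emerging on LTE treatment.

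LTE safety is a primary objective. The AE of special interest is hypocalcemia, which protocol 8.5.7 describes as a complication of the underlying disease when it is inadequately treated, and SAP 13.6.1 tabulates it by period. Hypocalcemia while waiting for the LTE would therefore appear as an LTE event on encaleret.

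**Working it through.** **1. AE classification.** Let L be the last Period 3 dose date, R the first LTE dose date, and g = R − L. The off-drug dates lie strictly between them, so there are g − 1.

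- Current rule: each of these dates is after the first Period 2 dose and before the last study dose + 30 days, so it is in the TEAE window. Each is on or after L + 1, so Table 2 assigns it to the LTE. All g − 1 are LTE TEAE dates.
- Period 1-2 rule applied to the same interval: L + 1 to L + 30 stay treatment-emergent, which is min(30, g − 1) dates. The rest, max(0, g − 31), do not.

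| Gap g (days) | Off-drug dates | LTE TEAE dates, current rule | Treatment-emergent under Period 1-2 rule | Not treatment-emergent |
|---|---|---|---|---|
| 30 | 29 | 29 | 29 | 0 |
| 46 | 45 | 45 | 30 | 15 |
| 60 | 59 | 59 | 30 | 29 |
| 90 | 89 | 89 | 30 | 59 |

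These are calendar dates, not AE counts, and the gap lengths are illustrative. Protocol 9.6 also stops counting TEAEs at 30 ± 7 days after the last dose. If that means the last dose before the gap, it agrees with the right-hand columns apart from its 7-day tolerance. The result is for AEs with a usable start date, since SAP 10.8 and 10.11 handle partial and missing dates separately.

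**2. Table 1 against Table 2.** On medications, SAP 10.7 says: "Each medication is mapped to a Period based on their start date and as per the rules defined in Table 1". Table 1 starts the LTE at its first dose, not at L + 1. Calcitriol restarted during a gap therefore maps to Period 2/3, while an AE on the same day maps to the LTE. The medication mapping itself is not in dispute.

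**3. Visit labels (secondary).** Study days for the LTE count from Period 2 Day 1 (SAP 10.4). The Week 24 target is 6 + 7 × 24 = 174. The formula 174 + 30 × month reproduces all eight Table 4 targets: 264, 354, 444, 534, 624, 714, 804 and 894. Each upper limit is the target + 45. Assume that the last Period 3 dose falls on Day 174.

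- *Months counted from the restart:* Month m falls on Day 174 + g + 30m. At g = 45, Month 3 is Day 264 + 45 = 309, still inside its window of 189-309. At g = 46 it is Day 310, labelled Month 6. Month 24 is Day 894 + 46 = 940, past the last window, which ends at 939. From 46 to 135 days every visit moves one label later. Restart-day labs, on Day 220-309, are then the only on-schedule value in the Month 3 window.
- *Sensitivity of the 46 days:* it becomes 39 if visits run 7 days late. With calendar months it is 45 at Month 3, falling to 35 at Month 24. It is 16 for a Month 24 visit at the end of the protocol's +30-day allowance.
- *Months counted from Week 24:* Month m falls on Day 174 + 30m whatever the gap, and every on-schedule visit is labelled correctly.

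The documents support both anchors. The Month 0 column, with its reconsent and restart note, points to the restart. The heading of SAP Table 11, protocol 4.1 and SAP 8.0 place the LTE after the Week 24 visit.

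**The case against.** The strongest reply is that the premise may simply be true. SAP version 3.0 was written after all subjects had completed Week 24 (13.7.1), so its authors may have known that nobody stopped. That may be so, but the sentence is a forward-looking assumption, whereas 13.7.1 records observed facts. Its statement that there were no early discontinuations does not settle whether someone who completed Week 24 then waited for the LTE.

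SAP 10.13 and 10.15 are in the contents list, but their text was not available here. The change history mentions subject-specific handling only for DXA and iPTH, but a rule for gaps cannot be excluded.

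The AE effect is also narrower than it first looks. In the first 30 off-drug days only the period label is wrong. Protocol 8.5.5 requires AE collection to 30 ± 7 days after the last dose; if that means the last Period 3 dose, few later events may be collected. Any overcount errs towards reporting more harm, in descriptive single-arm tables. These points limit the size but do not remove the misclassification.

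Two stronger readings are tempting. One is that a large share of participants had a gap, because the amendment that introduced the LTE and the restart text ("Amendment 6: Date 03 June 2021") also mentions "The first 7 participants who have completed CLTX-305-201 Period 2 and entered into Period 3". That shows the case was live, but seven of up to 16 is a count of people in Period 3, not of gaps; the documents do not say whether the LTE was open when each reached Week 24. The other is that LTE visits are mislabelled as such. That holds only under the restart anchor, which the documents leave open.

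**Conclusion.** The concern stands, conditionally, and centres on the AE rule. The SAP's premise conflicts with the protocol and with its own appendix. In the case they allow, the visible rules classify every dated off-drug AE as an LTE TEAE. On a 60-day gap, 29 of 59 off-drug dates would be treatment-emergent only because of this rule, and the other 30 would carry the wrong period. The number of participants affected is unknown and may be zero.

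The visit-label effect depends on an LTE anchor that the plan does not state, and its 46-day threshold is nominal. Week 24 efficacy and the paired t-tests, which cover Periods 2 and 3 only, are unaffected. Listings keep the recorded visit names, and LTE data go into a CSR addendum. The conclusion assumes that no rule in the unavailable SAP text already covers the case.

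**What to change.** First establish whether any participant had a gap. If none did, replace the general premise in 10.7 and 10.8 with a statement of that fact. That costs one sentence.

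Otherwise, for participants with a gap only:

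- Start the LTE in Table 2 at the first LTE dose.
- End the Period 3 TEAE window at the earlier of the last Period 3 dose + 30 days and the day before the first LTE dose, and map AEs in that span to Period 3.
- List AEs after that window and before the first LTE dose separately as not treatment-emergent, as between Periods 1 and 2.
- Reopen the TEAE window at the first LTE dose.
- State the anchor for LTE visits. Shift the Table 4 windows by the gap, with a Month 0 visit for restart labs, only if visits were scheduled from the restart. If they were scheduled from Week 24, the shift would itself cause errors: a 60-day shift makes the Month 3 window 249-369 (189 + 60 to 309 + 60), which would capture the Month 6 visit on Day 354.

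The cost is short SAP text and minor programming from two dates that the SAP already uses. Participants without a gap are unchanged.
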